3.2. STUDY CENTER

Up to five study centers

3.3. STUDY POPULATION

The target population for this study will be patients with locally advanced or metastatic solid tumors.

3.4. ELIGIBILITY CRITERIA

3.4.1. Inclusion Criteria

Subjects will be eligible for enrollment in the study only if they meet ALL the following criteria at time of Screening:

1. Age 18 years or older.
2. Histologically or cytological documented solid tumor.
3. Available tumor biopsy (most recent) for DRP® analysis.
4. Measurable disease by CT scan or MRI if possible.

-
5. Performance status of ECOG ≤ 1 .
 6. Recovered to Grade <1 or baseline from prior surgery or from acute toxicities of prior radiotherapy, or from treatment with cytotoxic, hormonal or biologic agents.
 7. ≥ 2 weeks must have elapsed since any prior surgery or therapy with G-CSF and GM-CSF.
 8. Patients with intracranial disease must be on stable or decreased level of steroid therapy (e.g. dexamethasone) for at least 7 days prior to baseline MRI. Non-enzymatic inducing anti-epileptic drugs are allowed.
 9. Adequate conditions as evidenced by the following clinical laboratory values:
 - a. Absolute neutrophils count (ANC) $\geq 1500/\text{mm}^3$ ($1.5 \times 10^3/\text{mL}$)
 - b. Hemoglobin $> 10.0 \text{ g/dL}$
 - c. Platelets $\geq 100,000/\text{mm}^3$ ($\geq 100 \times 10^9/\text{L}$)
 - d. Alanine aminotransferase (ALT) and aspartate aminotransferase (AST) $\leq 3 \times \text{ULN}$ or $\leq 5 \times \text{ULN}$ in presence of liver metastases
 - e. Serum bilirubin $\leq 1.5 \text{ ULN}$
 - f. Alkaline phosphatase $\leq 2.5 \times \text{ULN}$
 - g. Creatinine $\leq 1.5 \text{ ULN}$
 - h. Blood urea nitrogen (BUN) $\leq 2 \times \text{ULN}$.
 10. Life expectancy equal or longer than 3 months.
 11. The subject is willing to provide written informed consent to participate in the study after reading the informed consent form and the information provided and has had the opportunity to discuss the study with the investigator or designee.
 12. The subject is able to communicate satisfactorily with the investigator and to participate in, and comply with, the requirements of the study.
 13. The subject is able to understand the nature of the study and any potential hazards associated with participating in it.
 14. Negative pregnancy test for female subjects of childbearing potential. Women of childbearing potential (WOCBP) and Women of non-childbearing potential are eligible to participate. Both women of childbearing potential and women of non-childbearing potential should use an approved method of birth control and agree to continue to use this method for the duration of the study (and for 90 days after taking the last dose of study drug).

Acceptable methods of contraception include abstinence, female subject/partner's use of hormonal contraceptive (oral, implanted, or injected) in conjunction with a barrier method (WOCBP only) (e.g., diaphragm, cervical cap, male condom, and female condom and

spermicidal foam, sponges, and film), female subject/partner's use of an intrauterine device (IUD), or if the female subject/partner is surgically sterile for at least three months before screening or 2 years post-menopausal at time of screening. All male subjects/partners must agree to consistently and correctly use a condom for the duration of the study and for 90 days after taking the study drug. In addition, subjects may not donate sperm for the duration of the study and for 90 days after taking study drug.

3.4.2. Exclusion Criteria

Subjects meeting ANY of the following criteria at time of Screening will be excluded from enrollment:

1. Concurrent chemotherapy, radiotherapy, hormonal therapy, or other investigational drug except non-disease related conditions (e.g. insulin for diabetes) during study period.
2. Other malignancy with exception of curative treated non-melanoma skin cancer or cervical carcinoma in situ within 5 years prior to entering the study.
3. Any active infection requiring parenteral or oral antibiotic treatment.
4. History of coagulation or bleeding disorder or subject currently on therapeutic anticoagulant medication.

Note: Prophylactic doses of heparin or low molecular weight heparin are allowed.

5. Known HIV positivity.
6. Known active hepatitis B or C.
7. Clinically significant (i.e. active) cardiovascular disease:
 - a. Stroke within ≤ 6 months prior to day 1
 - b. Transient ischemic attack (TIA) within ≤ 6 months prior to day 1
 - c. Myocardial infarction within ≤ 6 months prior to day 1
 - d. Unstable angina
 - e. New York Heart Association (NYHA) Class II or greater congestive heart failure (CHF)
 - f. Serious cardiac arrhythmia requiring medication.
8. Other medications or conditions, including surgery, that in the Investigator's opinion would contraindicate study participation for safety reasons or interfere with the interpretation of study results.
9. Inability to take oral medication, or malabsorption syndrome or any other uncontrolled gastrointestinal condition (e.g., nausea, diarrhea, or vomiting) that might impair the bioavailability of 2X-121 and dovitinib.

10. Requiring immediate palliative treatment of any kind including surgery and/or radiotherapy.
11. Female patients who are pregnant or breast-feeding (pregnancy test with a positive result before study entry).

Table 4-2: Part 2 Dose Cohorts

Dose Cohort	Combination 2X-121 (BID administration) and Dovitinib
Cohort 1	2X-121 (MTD) + 300 mg dovitinib
Cohort 2	2X-121 (MTD) + 400 mg dovitinib
Cohort 3	2X-121 (MTD) + 500 mg dovitinib

Dovitinib will be administered once daily (morning) on a 5 days on/2 days off schedule. In a 28 day cycle, dovitinib will be administered C1D1 - C1D5, C1D8 - C1D12, C1D15 - C1D19, and C1D22 - C1D26.

[REDACTED]

[REDACTED]

- [REDACTED]
- [REDACTED]
- [REDACTED]
- [REDACTED]
- [REDACTED]
- [REDACTED]
- [REDACTED]

Once the MTD has been determined, subjects enrolled in lower dose cohorts will be allowed to escalate the dose to the MTD, if acceptable per the Investigator's discretion. Subjects will be eligible for continuing treatment in absence of progressive disease or unacceptable toxicity or withdrawal of consent.

An additional 3-6 patients will receive 2X-121 in combination with dovitinib once the MTD dose is determined.

Table 4-3: Schedule of Assessments – Part 1

Page 58 of 117

Table 4-4: Schedule of Assessments – Part 2

Study Phase	Screening Phase	Treatment Phase								Follow-Up Phase	
		Treatment Cycle 1 (28 Days)			Treatment Cycle 2 (28 Days)			Subsequent Treatment Cycles (28 Days)			
Visit	SV	C1D1	C1D7	C1D15	C2D1	C2D7	C2D15	CXD1	CXD15	EOT	FU [16]
Window	Within 28 Days of C1D1		±1 Day	±1 Day	±1 Day	±1 Day	±1 Day	±1 Day	±1 Day	30 Days (±7) after last treatment dose	Every 3 months after EOT
[REDACTED]											
[REDACTED]	X										
[REDACTED]	X										
[REDACTED]	X										
[REDACTED]	X										
[REDACTED]	X	X	X	X	X		X	X		X	
[REDACTED]	X	X [5]	X [5]	X [5]	X [5]	X [5]	X [5]	X [5]	X [5]	X [5]	
[REDACTED]	X	X		X[6]	X[6]		X[6]	X[6]	X[6]	X	
[REDACTED]	X	X			X			X		X	
[REDACTED]	X	X			X			X		X	
[REDACTED]		X									X
[REDACTED]	X	X	X	X	X	X	X	X	X	X	X
[REDACTED]		X	X	X	X	X	X	X	X	X	X
[REDACTED]											
[REDACTED]	X [8]							X [7]		X [7]	
[REDACTED]	X [8]							X [7]		X [7]	
[REDACTED]	X [8]							X [7]		X [7]	
[REDACTED]											
[REDACTED]	X	X	X	X	X	X	X	X	X	X	
[REDACTED]	X	X		X	X		X	X	X	X	
[REDACTED]	X	X			X			X		X	
[REDACTED]	X	X								X	
[REDACTED]		X	X	X	X			X			
[REDACTED]	X										
[REDACTED]											
[REDACTED]											
[REDACTED]											
[REDACTED]											
[REDACTED]		X		X	X		X	X	X		

Page 60 of 117

4.2. SCREENING PHASE

The subject (or Legally Acceptable Representative (LAR)) will sign and date the informed consent form (ICF) and Health Insurance Portability Accountability Act (HIPAA) authorization (according to site policy and practices) prior to any study-related procedures. All study centers will be instructed to maintain the study-specific screening and enrollment logs at their sites.

4.2.1. Screening Visit: Up to 28 days

Subjects will be screened for enrollment within 28 days prior to Treatment Cycle 1, Day 1.

The assessments described in this section will be the same for both Part 1 and Part 2 of the study, unless otherwise noted.

Subjects will be screened in accordance with predefined entrance criteria as described in [Section 3.4](#). The following procedures will be performed at Screening:

- [REDACTED]
- [REDACTED]
- [REDACTED]
- [REDACTED]
- [REDACTED]
- [REDACTED]
- [REDACTED]
- [REDACTED]
- [REDACTED]
- [REDACTED]
- [REDACTED]
- [REDACTED]
 - [REDACTED]
 - [REDACTED]
 - [REDACTED]
[REDACTED]
- [REDACTED]
 - [REDACTED]
 - [REDACTED]
 - [REDACTED]

■ [REDACTED]

All subjects who fail to meet eligibility criteria are considered screen failures and are exited from the study without further evaluation.

Note: If a subject initially fails to meet inclusion/exclusion criteria and is later reconsidered for participation, the subject will be re-consented and assigned a new unique identification number at the time of re-screening. Subjects who fail their first screening attempt may be re-screened a maximum of once and may be enrolled if they are found to meet all inclusion and no exclusion criteria when re-screened.

All screening information for subjects who meet eligibility criteria will be transcribed onto the appropriate page of the Case Report Form (CRF). See [Section 7.2.1](#) for procedures for documenting screening failures.

4.3. TREATMENT PHASE

Subjects who meet all eligibility criteria during Screening are to be treated.

Each treatment cycle will consist of 28 days.

4.3.1. Treatment Cycle 1

- [REDACTED] ■ [REDACTED]
- [REDACTED]
- [REDACTED]
 - [REDACTED]
 - [REDACTED]
 - [REDACTED]
 - [REDACTED]
 - [REDACTED]
 - [REDACTED]
 - [REDACTED]
 - [REDACTED]
 - [REDACTED]
 - [REDACTED]
 - [REDACTED]
 - [REDACTED]

[REDACTED]

[REDACTED]

- [REDACTED]
- [REDACTED]
- [REDACTED]
- [REDACTED]

[REDACTED]

[REDACTED]

- [REDACTED]
- [REDACTED]
- [REDACTED]
- [REDACTED]
- [REDACTED]
- [REDACTED]
- [REDACTED]

[REDACTED]

[REDACTED]

- [REDACTED]
- [REDACTED]
- [REDACTED]
- [REDACTED]
- [REDACTED]
- [REDACTED]
- [REDACTED]
- [REDACTED]

4.3.2. Treatment Cycle 2

[REDACTED]

[REDACTED]

- I [REDACTED]
- I [REDACTED]
- I [REDACTED]
- I [REDACTED]
- I [REDACTED]
- I [REDACTED]
 - I [REDACTED]
 - I [REDACTED]
- I [REDACTED]
- I [REDACTED]
- I [REDACTED]

[REDACTED] [REDACTED]

[REDACTED]

- I [REDACTED]
- I [REDACTED]
- I [REDACTED]
- I [REDACTED]
 - I [REDACTED]

[REDACTED] [REDACTED]

[REDACTED]

- I [REDACTED]
- I [REDACTED]
- I [REDACTED]
- I [REDACTED]
 - I [REDACTED]
- I [REDACTED]
- I [REDACTED]

4.3.3. Subsequent Treatment Cycles

Subjects will be eligible for continuing treatment in absence of progressive disease or unacceptable toxicity or withdrawal of consent.

[REDACTED]

[REDACTED]

[REDACTED]

- [REDACTED]
- [REDACTED]
- [REDACTED]
- [REDACTED]
- [REDACTED]
- [REDACTED]
 - [REDACTED]
 - [REDACTED]
 - [REDACTED]
- [REDACTED]
 - [REDACTED]
 - [REDACTED]
- [REDACTED]
- [REDACTED]
- [REDACTED]

[REDACTED]

[REDACTED]

[REDACTED]

- [REDACTED]
- [REDACTED]
- [REDACTED]
 - [REDACTED]
- [REDACTED]

■ [REDACTED]

4.4. FOLLOW-UP PHASE

4.4.1. End of Treatment Visit (EOT)

An end of treatment visit will be conducted 30 (\pm 7) days after last treatment dose (i.e., after last dose of 2X-121).

The assessments performed at this visit will include:

- [REDACTED]
- [REDACTED]
- [REDACTED]
- [REDACTED]
 - [REDACTED]
 - [REDACTED]
 - [REDACTED]
 - [REDACTED]
- [REDACTED]
- [REDACTED]
- [REDACTED]
- [REDACTED]
 - [REDACTED]
 - [REDACTED]
 - [REDACTED]

4.4.2. Follow Up Visit (FU)

Follow-up visits will be done for survival status, by clinic visits or phone or another method of contact at least every 3 months from the date of treatment discontinuation. All subsequent anti-cancer treatments are to be reported.

All patients are to be followed for 2 years or until death whichever comes first.

The assessments performed at these visits will include:

- [REDACTED]
- [REDACTED]
- [REDACTED]

4.5. UNSCHEDULED VISITS

In the event that the subject will return to clinic at a time other than a regularly scheduled study visit, the visit will be regarded as an unscheduled visit. This includes when subjects require rescue therapy or need interim care due to chronic illness. Assessments at unscheduled visits are at the discretion of the Investigator. All pertinent findings, including adverse events or changes in medications, will be noted in the CRF.

5. SUBJECT COMPLETION, WITHDRAWAL AND CRITERIA FOR STOPPING THE STUDY

5.1. SUBJECT COMPLETION

5.1.1. Definition of Study Treatment Completion

5.1.1.1. End of Treatment (EOT) Completion

A subject is considered to have completed the treatment phase once they complete the EOT visit conducted 30 (± 7) days after the last treatment visit (i.e., after last dose of 2X-121).

5.1.1.2. End of Follow-Up (EOFU) Completion

A subject is considered to have completed the follow-up phase once all survival follow-up visit assessments after treatment discontinuation have been performed or until death, whichever occurs first.

5.2. SUBJECT WITHDRAWAL

At any point during the study all subjects have the right to withdraw without prejudice to future care. Documentation to whether or not each subject completed the clinical study will be recorded. If for any subject, study treatment was discontinued, the reason(s) will be documented.

5.2.1. Subject Discontinuation

The Investigator can discontinue a subject at any time if in their clinical judgment considers to be medically necessary. Investigators considering discontinuing study treatment should contact the medical monitor prior to such discontinuation. Subjects who have study treatment discontinued will continue to be followed, per protocol, whenever possible. Subjects who have study treatment discontinued due to a serious adverse event will be followed until resolution or stabilization of the event as described in [Section 9.4.1](#) (SAE Follow-Up).

5.2.2. Subject Replacement

This study will follow a 3+3 design during Part 1 and Part 2. Three subjects within a dose level must be observed for one cycle (14 days) before accrual to the next higher dose level may begin. If a subject is withdrawn from the study prior to completing one cycle of therapy for any reason other than experiencing a DLT, an additional subject may be added to that dose level.

Note: Subjects who discontinue treatment prior to completing one cycle of therapy due to experiencing a DLT will not be replaced.

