3. STUDY DESIGN

3.1. GENERAL SCHEMA

This is a Phase Ib, two-part, multi-center study. In Part 1, the study will evaluate the safety and tolerability, antitumor activity, pharmacokinetics, and determine the maximum tolerated dose (MTD) of 2X-121 monotherapy (at BID regimen) in patients with advanced solid tumors. In Part 2, the study will evaluate safety and tolerability, antitumor activity, and pharmacokinetics of 2X-121 (MTD) and dovitinib as combination therapy, and determine the MTD of dovitinib when given in combination with the MTD of 2X-121 determined in Part 1.

Part 1

This part of the study will follow an accelerated titration method followed by a standard “3+3” design to determine the MTD of 2X-121. The MTD is defined as one dose level (cohort) below the dose in which dose limiting toxicities (DLTs) were observed in $\geq 33\%$ of the participants.

The calculation of the sample size for this trial is based on the traditional 3 + 3 dose escalation scheme which is conducted as follows:

- Subjects are treated in cohorts of one (Cohort 1) or three (Cohorts 2-3) subjects, each receiving the same dose. For the assessment of a DLT, subjects are observed for 14 days.
- In Cohort 1, if the one subject does not exhibit a DLT, the next cohort of three subjects will receive the next higher dose (Cohort 2). In Cohort 2, if none of the three subjects exhibits a DLT, the next cohort of three subjects will receive the next higher dose (Cohort 3).
- Otherwise, if at least one subject of a cohort exhibits a DLT, a further cohort of three subjects is treated at the same dose level (cohort) without escalating the dose.
- If exactly one out of the six subjects treated at this dose exhibits a DLT, the trial continues as planned at the next higher dose level (cohort).
- If two or more subjects out of the six subjects treated at this dose exhibit a DLT, the dose escalation stops at that level and the next lower dose is considered as the MTD. When the escalation has stopped, additional subjects will be treated at the MTD to a total of six subjects.

[REDACTED]

[REDACTED]

[REDACTED]

[REDACTED]

[REDACTED]

[REDACTED]

[REDACTED]

[REDACTED]

[REDACTED]

[REDACTED]

[figure not shown]
[REDACTED]

- [REDACTED]
[REDACTED]
- [REDACTED]
[REDACTED]
- [REDACTED]
- [REDACTED]
[REDACTED]
- [REDACTED]
[REDACTED]
- [REDACTED]
[REDACTED]

Part 2

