8.3. SAMPLE SIZE DETERMINATION AND RATIONALE

A sample size of up to 16 subjects in Part 1 and in up to 24 subjects in Part 2 will be used in this trial. This sample size is selected based on the conventional 3+3 study design and not based on statistical power calculation; it is deemed adequate to provide clinically meaningful descriptive results consistent with study objectives.

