2. PROTOCOL DESIGN

2.1 Design Overview

2.1.1 Study Design

This is a Phase Ib, two-part, multi-center study. In Part 1, the study will evaluate the safety and tolerability, antitumor activity, pharmacokinetics, and determine the maximum tolerated dose (MTD) of 2X-121 monotherapy (at BID regimen) in patients with advanced solid tumors. In Part 2, the study will evaluate the safety and tolerability, antitumor activity, pharmacokinetics and determine the MTD of dovitinib when given in combination with the MTD of 2X-121 determined in Part 1.

Part 1

This part of the study will follow an accelerated titration method followed by a standard “3+3” design to determine the MTD of 2X-121. The MTD is defined as one dose level (cohort) below the dose in which dose limiting toxicities (DLTs) were observed in $\geq 33\%$ of the participants.

The calculation of the sample size for this trial is based on the traditional 3 + 3 dose escalation scheme which is conducted as follows:

- Subjects are treated in cohorts of one (Cohort 1) or three (Cohorts 2-3), each receiving the same dose. For the assessment of a DLT subjects are observed for 14 days
- In Cohort 1, if the one subject does not exhibit a DLT, the next cohort of three subjects received the next higher dose. In Cohorts 2-3, if none of the three subjects of a cohort exhibits a DLT, the next cohort of three subjects receives the next higher dose.
- Otherwise, if at least one subject of a cohort exhibits a DLT, a further cohort of three subjects is treated at the same dose level (cohort) without escalating the dose.
- If exactly one out of the six subjects treated at this dose exhibits a DLT, the trial continues as planned at the next higher dose level (cohort).
- If two or more subjects out of the six subjects treated at this dose exhibit a DLT, the dose escalation stops at that level and the next lower dose is considered as the MTD. When the escalation has stopped, additional subjects will be treated at the MTD to a total of six subjects.

The dose levels to be evaluated in Part 1 are shown below:

Dose Cohort	2X-121 Monotherapy Dose (BID)
Cohort 1	600 mg (morning dose: 200 mg + evening dose: 400 mg)
Cohort 2	800 mg (morning dose: 400 mg + evening dose: 400 mg)
Cohort 3	1000 mg (morning dose: 400 mg + evening dose: 600 mg)

On Day 1 of first treatment cycle (C1D1), patients will be administered 2X-121 monotherapy as oral capsules taken twice daily. Each treatment cycle will consist of 28 days.

[REDACTED]

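### The visible text gives two incompatible rules for the first escalation in Part 1: Protocol 5.2.2 requires three observed subjects, while Protocol 3.1, the synopsis and SAP 2.1.1 require one

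*Protocol*

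**What the plan says.** Protocol 5.2.2 first sets its scope, "This study will follow a 3+3 design during Part 1 and Part 2", and then states the condition for moving up: "Three subjects within a dose level must be observed for one cycle (14 days) before accrual to the next higher dose level may begin". The section contains no exception for the first cohort of Part 1.

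Protocol 3.1 describes Part 1 differently: "This part of the study will follow an accelerated titration method followed by a standard “3+3” design to determine the MTD of 2X-121". On cohort size it says "Subjects are treated in cohorts of one (Cohort 1) or three (Cohorts 2-3) subjects, each receiving the same dose", and on the first escalation "In Cohort 1, if the one subject does not exhibit a DLT, the next cohort of three subjects will receive the next higher dose". The synopsis carries the same rules. SAP 2.1.1 agrees: "Subjects are treated in cohorts of one (Cohort 1) or three (Cohorts 2-3), each receiving the same dose", and "In Cohort 1, if the one subject does not exhibit a DLT, the next cohort of three subjects received the next higher dose".

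After any DLT in a cohort, Protocol 3.1 and SAP 2.1.1 add three subjects at the same dose. They then continue if exactly one of six has a DLT and stop if two or more of six do. Once escalation stops, the MTD level is topped up to six.

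Protocol 8.3 gives "A sample size of up to 16 subjects in Part 1" and up to 24 in Part 2. The synopsis and SAP 3 give the same figures. All three attribute them to the 3+3 design and not to a power calculation.

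**The concern.** Take the commonest early situation: one subject has been treated at the first dose, 14 days have passed, and there is no DLT. Protocol 3.1 opens Cohort 2. Protocol 5.2.2 forbids it until two more subjects have been observed at the same dose. Following either section breaks the other, and Protocol 11.4 obliges investigators to follow the protocol as written.

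This decision determines when three subjects are exposed to the next dose. It is also part of the algorithm that yields the MTD, so the operating characteristics of the primary outcome depend on which rule is applied.

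The point concerns only the number of subjects needed to escalate. It does not rely on the cycle-length or replacement wording in the same section.

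**Working it through.** **Inputs.** Part 1 has three dose levels (Protocol synopsis and 6.1, SAP 2.1.1). Starting cohort sizes are 1, 3, 3 (Protocol 3.1, SAP 2.1.1) or three at every level (Protocol 5.2.2). Three subjects are added after a DLT and the MTD level is topped up to six (Protocol 3.1). The documents give no true DLT rate, so 10 to 40% is assumed.

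**1. The stated maxima.** The documents do not show how they were derived, so the possible escalation paths were counted.

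- One-subject rule, Cohort 1 growing literally from 1 to 1+3 = 4: 4+6+6 = **16**, the stated cap.
- Part 2, three per level, plus the upper end of the 3 to 6 extra subjects at the MTD: 6+6+6+6 = **24**, also the stated figure.
- Three-subject rule in Part 1: 6+6+6 = **18**.
- One-subject rule with Cohort 1 filled to six after a DLT: 6+6+6 = **18**.

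The fourth line matters because the written continue and stop rules refer only to six subjects. With Cohort 1 at four, no visible rule covers 1 DLT in 4. The match to 16 therefore requires that Cohort 1 stay at four and that 1 of 4 permit escalation. The second condition is compatible with the 33% threshold (1/4 = 25%) but is not written.

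**2. Chance that Cohort 2 opens.** Let p be the true 14-day DLT rate at the Cohort 1 dose and q = 1 − p.

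- Three-subject rule (0/3, or 1/3 then 0/3): q³ + 3pq²·q³ = q³ + 3pq⁵
- One-subject rule (a), only 0/1 escalates: q
- One-subject rule (b), filled to six and 1/6 continues: q + pq⁵
- One-subject rule (c), expanded to four and 1/4 continues: q + pq³

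Example at p = 0.30: the three-subject rule gives 0.343 + 0.9 × 0.168 = 0.494. The one-subject versions give (a) 0.700, (b) 0.700 + 0.3 × 0.168 = 0.750 and (c) 0.700 + 0.3 × 0.343 = 0.803.

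| Assumed p | Three-subject | One-subject (a) | One-subject (b) | One-subject (c) |
|---|---|---|---|---|
| 10% | 91% | 90% | 96% | 97% |
| 20% | 71% | 80% | 87% | 90% |
| 30% | 49% | 70% | 75% | 80% |
| 40% | 31% | 60% | 63% | 69% |

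The gap (one-subject minus three-subject) is about −1 to +7 points at 10%, 9 to 19 at 20%, 21 to 31 at 30% and 29 to 38 at 40%.

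**3. How often the three-subject rule would exceed 16.** Its possible totals are 6, 9, 12, 15 and 18, so only 18 exceeds the cap. Reaching 18 requires Cohort 1 to expand and still escalate (probability e = 3pq⁵). Then either Cohort 2 does the same, with Cohort 3 expanded or topped up to six, or Cohort 2 clears at 0/3 and Cohort 3 stops escalation, which tops Cohort 2 up to six. With the same p at every level, the probability is e × [e + q³(1 − q³ − e)]:

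- p = 0.10: 0.177 × (0.177 + 0.729 × 0.094) = 0.044
- p = 0.20: 0.197 × (0.197 + 0.512 × 0.291) = 0.068
- p = 0.30: 0.151 × (0.151 + 0.343 × 0.506) = 0.049

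That is about 4 to 7%.

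**The case against.** The best defence is that the specific rule overrides the general one. The design section, the synopsis and the SAP agree, name accelerated titration and state the Cohort 1 rule expressly. The outlier is one sentence under a heading about subject replacement. That agreement is real, but 5.2.2 is not merely general: it names Part 1, is mandatory in tone and states a condition for opening the next dose level. No visible text gives precedence to either section.

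Text directly after the escalation bullets is redacted. The study-design figure, Section 4.1 and Table 4-1 are not in the public text. It can therefore be said that 5.2.2 itself contains no exception, but not that the full protocol lacks one. A clarification elsewhere would still leave 5.2.2 needing correction.

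Two stronger readings are tempting, and the documents support neither.

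- A reader might infer that the cap of 16 fits only the one-subject rule, so that the sample size fails under the other. The one-subject scheme also reaches 18 if Cohort 1 is filled to six. The cap is an upper limit for a descriptive study, not a power-based number. Most three-subject paths stay within it, and replacements under 5.2.2 could take either count higher.
- A reader might infer that sites will escalate by different rules within the trial. No visible text says that individual sites open cohorts independently. The probabilities above compare two rules; they do not measure the effect of a stray sentence.

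**Conclusion.** The concern holds as an inconsistency in the escalation rule. As written, 5.2.2 and the design text cannot both be followed at the first escalation of Part 1, and the visible text does not say which governs. It needs correction because it is a decision rule behind the primary outcome and behind subject exposure.

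Its size depends on the unknown DLT rate and on an unwritten step. At 10% the rules differ little; at 30 to 40% the chance of opening Cohort 2 differs by about 20 to 30 points or more, whichever handling of a Cohort 1 DLT is assumed. The agreement of 16 with 4+6+6 is consistent with the one-subject scheme but does not prove it, since it rests on a 1-of-4 rule that is not visible. Which rule is right is not judged here.

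**What to change.** Three linked edits in the next amendment:

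1. Reconcile Protocol 5.2.2 with Protocol 3.1, the synopsis and SAP 2.1.1 so that one stated number of observed subjects governs the opening of Part 1 Cohort 2. State it expressly for Part 1 Cohort 1 and separately for all other dose levels.
2. Reconcile the continue and stop wording, which covers only six subjects, with the size that Cohort 1 reaches after a DLT.
3. Recount the Part 1 maximum under the reconciled rules and, if it is not 16, restate it in the synopsis, Protocol 8.3 and SAP 3.

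The sponsor must decide which rule applies. The cost is a sentence or two in the protocol and SAP, and possibly one changed number. No new procedure or data collection is needed, though a restated cap of 18 would allow two more subjects.
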